8.8.1.2. Treatment Phase

Study Visit 2 (Baseline-Day 1)

- Inclusion/Exclusion review
- Randomize
- Vital signs
- Interval history

- SBQ-R
- Concomitant medication review
- Brief Pain Inventory (BPI)
- SF-36
- MSIS-29
- EQ-5D
- SBQ-R
- Hematology, chemistry, and urinalysis labs
- Urine pregnancy test (urine β -hCG) (in females)
- Cognitive Tests (SDMT and SRT)
- MS Functional Composite (MSFC)
- EDSS by blinded neurologist
- Adverse event monitoring
- Study drug dispensing

Study Visit 3 (Week 4)

- Physical examination
- Body weight
- Vital signs
- Interval history
- Adverse event review
- Concomitant medication review
- Relapse assessment
- BPI
- SBQ-R
- Hematology, chemistry, and urinalysis labs
- Serum pregnancy test (in females)
- ECG (12-lead)
- Study drug accountability

Study Visit 4 (Week 8)

- Physical examination
- Body weight
- Vital signs
- Interval history
- Adverse event review
- Concomitant medication review
- Relapse assessment
- BPI
- SBQ-R
- Hematology, chemistry, and urinalysis labs
- Serum biomarker samples
- Serum pregnancy test (in females)
- Plasma sample for PK
- ECG (12-lead)
- Study drug accountability

Study Visit 5 (Week 12)

- Physical examination
- Body weight
- Vital signs
- Interval history
- Adverse event review
- Concomitant medication review
- Relapse assessment
- BPI
- SBQ-R
- Hematology, chemistry, and urinalysis labs
- Serum pregnancy test (in females)
- ECG (12-lead)
- Study drug accountability

Study Visit 6 (Week 24)

- Physical examination
- Body weight
- Vital signs
- Interval history
- Adverse event monitoring
- Concomitant medication review
- Relapse assessment
- Cognitive tests (SDMT and the SRT)
- BPI
- SF-36
- MSIS-29
- EQ-5D
- SBQ-R
- Hematology, chemistry, and urinalysis labs
- Serum pregnancy test (in females)
- ECG (12-lead)
- MSFC
- EDSS by blinded neurologist
- Brain MRI
- OCT
- Return of used/unused study drug bottles, study drug accountability and compliance check
- Dispense study drug

Study Visit 7 (Week 36)

- Physical examination
- Body weight
- Vital signs
- Interval history
- Adverse event review
- Concomitant medication review

- Relapse assessment
- BPI
- SBQ-R
- Hematology, chemistry, and urinalysis labs
- Serum pregnancy test (in females)
- ECG (12-lead)
- Study drug accountability

Study Visit 8 (Week 48)

- Physical examination
- Body weight
- Vital signs
- Interval history
- Adverse event monitoring
- Concomitant medication review
- Relapse assessment
- Cognitive tests (SDMT and SRT)
- BPI
- SF-36
- MSIS-29
- EQ-5D
- SBQ-R
- Hematology, chemistry, lipid profile, and urinalysis labs
- Serum biomarker samples
- Serum pregnancy test (in females)
- Plasma sample for PK
- ECG (12-lead)
- MSFC
- EDSS by blinded neurologist
- Brain MRI
- OCT

- Lumbar puncture (optional)
- Return of used/unused study drug bottles, study drug accountability and compliance check
- Dispense study drug

Study Visit 9 (Week 60)

- Physical examination
- Body weight
- Vital signs
- Interval history
- Adverse event review
- Concomitant medication review
- Relapse assessment
- BPI
- SBQ-R
- Hematology, chemistry, and urinalysis labs
- Serum pregnancy test (in females)
- ECG (12-lead)
- Study drug accountability

Study Visit 10 (Week 72)

- Physical examination
- Body weight
- Vital signs
- Interval history
- Adverse event monitoring
- Concomitant medication review
- Relapse assessment
- Cognitive tests (SDMT and the SRT)
- BPI
- SF-36
- MSIS-29

- EQ-5D
- SBQ-R
- Hematology, chemistry, and urinalysis labs
- Serum pregnancy test (in females)
- ECG (12-lead)
- MSFC
- EDSS by blinded neurologist
- Brain MRI
- OCT
- Return of used/unused study drug bottles, study drug accountability and compliance check
- Dispense study drug

Study Visit 11 (Week 84)

- Physical examination
- Body weight
- Vital signs
- Interval history
- Adverse event review
- Concomitant medication review
- Relapse assessment
- BPI
- SBQ-R
- Hematology, chemistry, and urinalysis labs
- Serum pregnancy test (in females)
- ECG (12-lead)
- Study drug accountability

Study Visit 12 (Week 96)

- Physical examination
- Body weight
- Vital signs

- Interval history
- Adverse event monitoring
- Concomitant medication review
- Relapse assessment
- Cognitive tests (SDMT and SRT)
- BPI
- SF-36
- MSIS-29
- EQ-5D
- SBQ-R
- Hematology, chemistry, lipid profile, and urinalysis labs
- Serum biomarker samples
- Serum pregnancy test (in females)
- Plasma sample for PK
- ECG (12-lead)
- MSFC
- EDSS by blinded neurologist
- Brain MRI
- OCT
- Lumbar puncture (optional)
- Return of used/unused study drug bottles, study drug accountability and compliance check

Follow-up Visit 13 (Week 100)

- Physical examination
- Body weight
- Vital signs
- Interval history
- Adverse event monitoring
- Concomitant medication review
- Relapse assessment
- SBQ-R

Unscheduled Visits**Relapse Evaluation**

Between scheduled study visits, subjects with new or significant worsening MS symptoms that last 24 hours in duration and occur in the absence of fever or infection should notify the Investigator immediately and be seen for an Unscheduled Relapse Evaluation Visit within 3 days of notifying the Investigator. The following assessment should be performed at the Relapse Evaluation Visit:

- Body weight
- Vital signs
- Interval history
- Adverse event monitoring
- Concomitant medication review
- SF-36
- MSIS-29
- SBQ-R
- BPI
- EDSS by blinded neurologist

Subjects continuing follow-up off study medication do not need to return for Unscheduled Relapse Evaluation Visits. If during a regularly scheduled study visit, a relapse episode is noted, complete the relapse evaluation assessments above along with the scheduled assessments for that study visit.

Semi-Annual Visits (for subjects who discontinue study medication)

Subjects who discontinue study medication and remain in the study for follow-up will be followed on a semi-annual basis (Week 24, 48, 72, and 96, relative to Baseline). The following assessments will be performed at each semi-annual visit:

- Relapse assessment
- Cognitive tests (SDMT and SRT)
- BPI
- SF-36
- MSIS-29
- EQ-5D
- SBQ-R
- MSFC

- EDSS
- Brain MRI
- OCT

Early Withdrawal Visit

Subjects who discontinue study medication and choose not to be followed on a semi-annual basis will undergo the following assessments:

- Physical examination
- Body weight
- Vital signs
- Interval history
- Adverse event monitoring
- Concomitant medication review
- Cognitive tests (SDMT and SRT)
- BPI
- SF-36
- MSIS-29
- EQ-5D
- SBQ-R
- Hematology, chemistry, lipid profile, and urinalysis lab
- Serum biomarker samples
- ECG (12-lead)
- MSFC
- EDSS
- Brain MRI
- OCT
- Lumbar puncture (optional)
- Return of used/unused study drug bottles, study drug accountability and compliance check

Laboratory Re-test visit

Subjects who have a clinically significant abnormal lab finding may return for a laboratory re-test visit and will have the following assessments performed at the discretion of the CSSPI:

- Interval history
- Hematology, chemistry, or urinalysis lab, as indicated

8.8.2. Procedures/Assessment Details

8.8.2.1. Informed Consent

The Clinical Study Site Principal Investigator (CSSPI) or a qualified designee (e.g., a licensed, qualified medical practitioner such as a physician's assistant or a nurse practitioner) listed on Form FDA 1572 will explain the study to the subject, answer all of the subject's questions, and obtain written informed consent before performing any study-related procedure. Informed Consent should be conducted in accordance with local requirements. Subjects should be able to verbally describe the benefits and risks associated with this study and what other treatment alternatives are available (as described in the consent form). Only subjects who provide informed consent, as assessed and documented by the Investigator, will be enrolled.

8.8.2.2. Medical History

A medical history including history of multiple sclerosis will be obtained by the CSSPI or qualified designee as listed on the Form FDA 1572. If the subject's historical MS care was provided at another institution or location, efforts must be made to obtain these outside records to verify that the subject meets all inclusion and none of the exclusion criteria. This must be accomplished during the screening period and added to the subject's medical record.

8.8.2.3. Prior/Concomitant Medication Review

Site study staff will record all medications used to treat multiple sclerosis taken within 1 month prior to screening visit in the CRF. Also, the following parameters will be recorded for all concomitant medications: drug name, route of administration, total daily dose, unit, frequency, start/stop dates, indication, and whether the medication was started after last dose of study medication. The concomitant medications will subsequently be coded using the World Health Organization Drug Dictionary (WHO-DD).

8.8.2.4. Relapse Assessment

Relapse Definition

A protocol-defined clinical relapse is defined as new or recurrent neurological symptoms, not associated with fever or infection, lasting for at least 24 hours, which is following a period of at least 30 days of stability or improvement. In addition, a protocol-defined clinical relapse requires an increase in the EDSS Functional System corresponding to symptom(s) of the relapse, or an increase in the overall EDSS secondary to a functional change related to symptom(s) of the relapse. Because relapse is an expected event in patients with MS, a relapse episode will not be considered an adverse event.

Relapse Treatment

Clinical relapses that meet the above definition may be treated with a course of corticosteroids at the investigator's direction. MRI studies must be postponed until 1 month after completion of any systemic (excludes topical, inhaled) corticosteroid treatment.

8.8.2.5. Physical Examination

The physical exams must be performed by the CSSPI or qualified designee (physician, physician's assistant or nurse practitioner) listed on the Form FDA 1572. Clinically significant changes from the signing of the informed consent form (ICF) should be captured as AEs in the CRF.

A complete physical examination includes the following assessments: general appearance, head, eyes, ears/nose/throat, neck, lymph nodes, skin, lungs, heart, abdomen, and musculoskeletal. If the subject is discontinued for any reason, every attempt should be made to perform a final physical examination.

8.8.2.6. Vital Signs, Height, and Weight

Blood pressure (BP), heart rate (HR) measurements will be taken. Respiratory rate and temperature will also be measured and all measurements will be recorded in the CRF. Clinically significant changes from the signing of the ICF should be captured as AEs in the CRF.

Weight will be measured in pounds or kilograms. Height will be recorded only at Visit 1 (screening).

8.8.2.7. Electrocardiogram (12-Lead ECG)

All subjects will have standard resting 12-lead ECGs performed and interpreted. A central facility will be used in this study for interpretation and analysis of ECGs. Subjects are to be supine for at least 5 minutes prior to ECG assessments. The time the ECG is performed will be recorded (using a 24-hour clock).

The CSSPI or a qualified designee listed on Form Food and Drug Administration (FDA) 1572 must review, initial, and date the report, which must be filed in the subject's study chart. If a CSSPI has reviewed, initialed and dated the original ECG tracing and the results on the tracing match those on the report, the report will be considered as reviewed and signed by the CSSPI. If the results vary, the CSSPI must also review, sign and date the report. Results will be captured in the subject's study chart, not in the CRF. Clinically significant findings from the screening report must be captured in the medical history. Any clinically significant changes compared with screening must be captured as an AE in the CRF.

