2	SPRINT-MS	To evaluate activity by measure brain volume by MRI	R,DB,PO	Up to 50 mg BID, placebo; oral	Planned 250	PPMS, SPMS 21 to 645 yo	96 weeks	Ongoing

CO=crossover; DB=double-blind; DM=diabetes mellitus; HV=healthy volunteers; MD=multiple dose; OLE=open-label extension; PC=placebo controlled, R=randomized.

The safety of ibudilast from 30 to 80 mg/d has been evaluated in single and multiple doses up to 14 days in healthy volunteers and diabetes mellitus Type 1 & 2 patients, chronic pain patients (diabetic neuropathy and complex regional pain syndrome) and opioid addict subjects. The dosage of 100 mg/d has been evaluated in single and multiple doses for up to 8 days (following 6 days of dose-incremental 40, 60 and 80 mg/d dosing at 2 days each) in healthy volunteers (HV) and diabetes mellitus (DM) Type 1 & 2 patients. In a phase 2 study MS trial, subjects received MN-166 30 or 60mg/d up to 2 years (96 weeks). An ongoing Phase 1b safety study to evaluate MN-166 in methamphetamine-dependent addicts recently completed enrollment. In this study, subjects received MN-166 40mg/d for 1 week and then 100 mg/d for 1 week. Other ongoing trials include dosage of 100 mg/d for 3 weeks to opioid addicts (with Columbia University/NYSPI expert investigators) and dosing for 8 weeks at 80 mg/d in chronic medication overuse headache (MOH) pain at the University of Adelaide with a prior AV411 investigator.

Notably, all of the trials listed in the table except for the first two have included all concurrent concomitant medications with ibudilast dosing at 80 or 100 mg/d. While pharmacokinetic drug-drug interactions have not been carefully assessed (or are in progress), there are no clear pharmacologic or safety interactions noted to date. Also, pharmacokinetics have been closely monitored in almost all of the trials and from the data of Study MN-166/AV411, the PK has generally been shown to be dose-proportional both within and between studies. Based on prior trials, steady state plasma C_{max} and AUC_{0-24h} levels at the highest dose (50 mg BID; 100 mg/d) are anticipated to be approximately 116 ng/ml (C_{max}) and 1613 ng*hr/ml (AUC_{0-24h}) (study AV411-026 HV group).

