11. ASSESSMENT OF SAFETY

11.1. Primary Safety Parameters

Safety will be assessed by the proportion of subjects with the following events:

- treatment emergent adverse events (TEAEs)
- treatment emergent serious adverse events (TESAEs)

Safety (relationship and severity) and tolerability will further be assessed by statistical and clinical review of AEs, laboratory values, ECGs, physical examinations, vital signs and weight.

During the study, if ≥ 5 new or enlarging T2 lesions should apply to any scans at any time points, the MSM should be notified and an evaluation of the subject should be made as to whether the subject may continue on study drug.

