$$[a_{ih} \ b_{ih}]^T \sim \mathcal{N}(\mathbf{0}, \mathbf{G}), [a_h \ b_h \ c_h \ d_h]^T \sim \mathcal{N}(\mathbf{0}, \mathbf{H}), \epsilon_{ij} \sim \mathcal{N}(0, \sigma^2 \mathbf{I}_i), \text{ and } [a_i \ b_i]^T \perp [a_h \ b_h \ c_h \ d_h]^T \perp \epsilon_{ij}.$$

If individual site variance components in \mathbf{H} are negligible, then the associated random effects will be omitted to simplify the model. In the case that all \mathbf{H} components are negligible, we will revert to Equation (1) for the analysis.

Primary Objective #2: To evaluate the safety and tolerability of ibudilast versus placebo.

The main assessment of safety will involve a comparison of treatment-related SAEs across the two treatment groups. This will be assessed in two ways. First, the percentage of subjects who experience any treatment-related SAE in each group will be compared using a chi-square test. Then, the rates of treatment-related SAEs in each group will be compared using a Poisson regression model. We will also assess the values of laboratory assessments over time across the two groups using a LMM. To assess tolerability, the percentage of subjects who complete the entire treatment period will be compared across the two groups using a chi-square test. Appropriate constraints for baseline imbalance will be used in all statistical models.

Major Secondary Objectives: *To evaluate the activity of ibudilast at two years versus placebo, as measured by:*

- (1) *Diffusion tensor imaging (DTI) in descending pyramidal white matter tracts*
- (2) *Magnetization transfer ratio (MTR) imaging in normal-appearing brain tissue*
- (3) *Retinal nerve fiber thickness as measured by optical coherence tomography (OCT)*
- (4) *Cortical atrophy as measured by cortical longitudinal atrophy detection algorithm (CLADA)*

The secondary objectives will be analyzed using a model similar to that described above for the assessment of BPF. An exception is the OCT analysis will require additional random effects for eyes nested within patients. Additional details are provided below. The baseline intercepts will again be constrained to be equal to account for baseline imbalance.

Other Objectives

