- Y_i represents the number of treatment related SAEs experienced by the i^{th} subject.
- T_i represents the number of months between the date of randomization and the date of last follow-up for the i^{th} subject.
- $x_{1i} = 1$ if i^{th} subject was thought to be receiving immunomodulation therapy at randomization (IFN/GA), and 0 if the subject was not thought to be receiving immunomodulation therapy
- $x_{2i} = 1$ if i^{th} subject was thought to have primary progressive MS at randomization, and 0 if the subject was thought to have secondary progressive MS
- $x_{3i} = 1$ if i^{th} subject was randomized to the Ibudilast group, and 0 if the subject was randomized to placebo group
- ϵ_i is random error for the i^{th} subject

To determine if the rate of treatment related SAEs differ across treatment group we will test the following hypothesis:

$$H_0: \beta_3 = 0 \text{ vs. } H_A: \beta_3 \neq 0$$

If the null hypothesis is rejected, the direction of β_3 will indicate the direction of the observed effect. Values of $\beta_3 > 0$ indicate an increased rate of treatment-related AEs associated with the Ibudilast group, while values of $\beta_3 < 0$ indicate a decreased rate of treatment-related AEs associated with the Ibudilast group.

Treatment-related SAEs will be analyzed in the same manner described above. Additional safety analyses will also assess all treatment-emergent AEs, treatment-emergent SAEs, unanticipated SAEs, and treatment-related & unanticipated SAEs in a similar manner.

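### ECG measurements have no stated route to the analysis data, and the SAP omits the by-arm laboratory model that the protocol promises

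*Combined protocol and SAP*

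**What the plan says.** **ECGs.** Protocol 11.1 names the proportions with treatment-emergent AEs and SAEs as the safety parameters. It then says that safety and "tolerability will further be assessed by statistical and clinical review of AEs, laboratory values, ECGs, physical examinations, vital signs and weight". Section 8.8.2.7 arranges central reading: "A central facility will be used in this study for interpretation and analysis of ECGs". On where the output goes, the same section sends results to the "study chart, not in the CRF. Clinically significant findings from the screening report must be captured in the medical history". One channel into the trial data is given for on-study findings: "Any clinically significant changes compared with screening must be captured as an AE in the CRF".

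**Laboratory values.** Protocol 12.1.2, under Primary Objective #2, states: "We will also assess the values of laboratory assessments over time across the two groups using a LMM". Section 12 describes the SAP as the comprehensive account of the statistical methods. SAP 7.2.1 sets out logistic and Poisson models for AEs and SAEs and then adds: "Additional safety analyses will also assess all treatment-emergent AEs, treatment-emergent SAEs, unanticipated SAEs", with one further SAE category. SAP 7.2.2 covers early discontinuation. Neither section mentions laboratory values or ECGs, and nor does the list of further analyses in SAP 8.5.

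**The concern.** The protocol makes two commitments that the operational text and the SAP do not carry through. If sites follow 8.8.2.7 and the statisticians follow the SAP, the trial ends with no comparison by arm of ECG intervals or of laboratory values.

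An AE-based analysis sees an ECG or laboratory change only after someone has judged it significant in one subject. A modest shift across a whole arm, with few individual values that stand out, is found by comparing the values themselves.

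This matters most for the liver tests. Protocol 4.6.2 says that MN-166 appeared to cause changes in AST, ALT and GGT, mostly transient. Prior exposure at the trial dose is also short. Section 4.5.1 says: "The dosage of 100 mg/d has been evaluated in single and multiple doses for up to 8 days". Its table lists ongoing 100 mg/d studies with planned durations up to 12 weeks, whereas this trial treats for 96 weeks.

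**Working it through.** The plan gives no figure to reproduce on this point. The check is a trace of each measurement from collection to analysis, followed by a count.

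**Step 1. Trace the data.**

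| Measurement | Where the values go | Protocol commitment | Analysis in the SAP |
|---|---|---|---|
| ECG | Study chart, not CRF; centrally read; no transfer stated (8.8.2.7) | Review in 11.1 | None, except as AEs |
| Laboratory values | Central laboratory (8.8); nothing keeps them out of the database | Review in 11.1; mixed model in 12.1.2 | None, except as AEs |
| Vital signs, including heart rate | CRF (8.8.2.6) | Review in 11.1 | None named |
| BPF, cortical thickness, DTI, MTR, OCT | Transfer to the DCC described (SAP 2.1, 3.1 to 3.4) | Primary and major secondary endpoints | SAP 7.1, 8.1 to 8.4 |

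The first two rows are different faults. For ECGs, the data route is unstated and the SAP has no analysis. For laboratory values, the analysis was written down in the protocol and is absent from the SAP.

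**Step 2. Can SAP 8.5 be read as restoring the laboratory model?** Its list is open-ended, so it does not forbid one. However, it does not name laboratory values, and it says that the analyses it covers stay out of the final study report. That does not discharge a commitment made under a primary objective.

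**Step 3. Count the assessments (Table 1, 250 subjects).**

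- ECGs: screening plus Weeks 4, 8, 12, 24, 36, 48, 60, 72, 84 and 96 make 11 per subject. 11 × 250 = 2,750, of which 10 × 250 = 2,500 are post-baseline.
- Safety laboratory draws: the same 11 visits plus Baseline make 12 per subject. 12 × 250 = 3,000.

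Both totals are ceilings. Protocol 12.1.3 assumes 10% dropout, and Table 2 schedules no ECG or safety laboratory test at visits after study drug is stopped.

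**Step 4. What could be estimated.** The documents give no SD for change in QTcF, so I assume 15 to 20 ms. The half-width of a 90% interval for the arm difference at one visit is 1.645 × SD × √(2/n).

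- n = 125 per arm: 1.645 × √(2/125) = 0.208, giving 3.1 ms (SD 15) to 4.2 ms (SD 20).
- n = 112 per arm (125 × 0.9, rounded down): 1.645 × √(2/112) = 0.220, giving 3.3 to 4.4 ms.

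This shows the precision available from ECGs already scheduled. It is not evidence of harm.

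**The case against.** The case on the other side is substantial, and most of it stands.

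- **The primary safety assessment is intact.** A reader might infer that Primary Objective #2 depends on this review. It does not. Its endpoints are the proportions with treatment-emergent AEs and SAEs and with early discontinuation. Section 11.1 presents the ECG and laboratory review as a further step that is partly clinical.
- **The laboratory data are not shown to be missing.** A reader might infer that the laboratory comparison is impossible. A central laboratory runs the tests, and the commitment in 12.1.2 has not been withdrawn. This is a SAP omission.
- **Absence from the CRF is not absence from every database.** The central ECG facility may hold an electronic file. The SAP describes transfers only for imaging endpoints, and it describes none for laboratory data either, so its silence on ECGs proves little. The text supports no more than that no route is stated.
- **Marked abnormalities are still seen.** Clinically significant ECG and laboratory findings count as AEs. AEs are compared by arm in SAP 7.2.1 and tabulated quarterly by blinded group for the Medical Safety Monitor (SAP 10.3). Section 8.6.2 sets numerical laboratory limits that trigger retesting and stopping, and resulting discontinuations feed the tolerability endpoint. Heart rate is already in the CRF as a vital sign.
- **Prior ECG experience is reassuring.** Section 4.6.2 reports no apparent significant effect on blood pressure, heart rate or ECGs. The QTcF exclusion above 450 ms is an eligibility criterion and is not described as a drug effect.

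None of this reconciles 11.1 with 8.8.2.7, or 12.1.2 with SAP 7.2. Nor does it supply a comparison of values below the level that a site would report. The earlier ECG experience does not extend to 96 weeks at 100 mg/d.

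**Conclusion.** Two inconsistencies stand on the text. The protocol promises a statistical review of ECGs whose results it keeps out of the CRF, with no stated route to the DCC. It also promises a by-group laboratory model that the SAP leaves out.

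The loss is limited to a by-arm comparison of ECG intervals, including QTcF, and of laboratory values, for shifts that no site calls significant. It weighs more for AST, ALT and GGT than for ECGs, given what section 4.6.2 reports about each. In scale, up to 2,750 ECGs have no stated route to analysis and up to 3,000 laboratory draws have no analysis in the SAP, both before dropout. Those counts come from Table 1; only the illustrative QTcF precision rests on an assumed SD.

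The documents do not support a conclusion that the safety objective fails, that the laboratory data are unavailable, or that a serious signal would go unseen. The point deserves correction because the commitments are the plan's own and the remedy is small.

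**What to change.** 1. **Laboratory values.** Add to SAP 7.2 the mixed model by arm that protocol 12.1.2 already promises. Name the analytes, with AST, ALT and GGT among them. State which of the two pre-dose draws (screening or Day 1) serves as baseline.
2. **ECGs.** In 8.8.2.7, state an electronic transfer of the central facility's measurements to the DCC at each visit. Add to SAP 7.2 a by-arm summary of change from screening, including QTcF. Screening is the only scheduled pre-treatment ECG.
3. **If these analyses are not intended**, amend protocol 11.1 and 12.1.2 so that they match 8.8.2.7 and the SAP.

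Counts by arm against the protocol's existing laboratory limits, and additions to the DSMB report, would be useful but are optional because the plan does not promise them.

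The cost is one data-transfer agreement with a facility that already reads the ECGs, and a few SAP tables. No visit, test or procedure is added.
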